legally authorized representative of the subject)	
Exclusion Criteria:	
1. Previous myocardial infarction2. Left bundle branch block (LBBB)3. Previous coronary artery bypass graft surgery (CABG)4. Major hemodynamic instability or uncontrolled ventricular arrhythmias5. Known contraindication to CMR (e.g. pacemaker)6. Patients with known thyroid disease, or known allergy to iodide7. Subjects with past or current renal impairment requiring dialysis8. Pregnant or females of childbearing potential9. Body weight > 120 kg or Body Mass Index (BMI) > 35 kg/m²10. Use of investigational drugs or devices within 30 days prior to enrollment into the study11. Life expectancy of less than 1 year due to non-cardiac pathology12. Any clinically significant abnormality identified at the time of screening that in the judgment of the Investigator or any sub-Investigator would preclude safe completion of the study
Investigational product, dosage and mode of administration:	FDY-5301 0.5 mg/kg, 1.0 mg/kg, 2.0 mg/kg or placebo will be administered intravenously (IV) by bolus injection between an hour and 5 minutes prior to coronary artery reperfusion.
Duration of treatment:	Treatment is a single IV bolus administration of study drug. Each subject will be involved up to 6 months from screening until study exit.
Reference therapy, dosage and mode of administration:	Placebo (normal saline for injection). Placebo will be indistinguishable from FDY-5301.
Statistical methods:	The primary outcome for this study will be the combined number and incidence rate of

several arrhythmias of interest that occur in each group over a 14 day period post-study drug. These arrhythmias including ventricular fibrillation, sustained ventricular tachycardia (≥ 125 BPM, ≥ 30 seconds), non-sustained ventricular tachycardia (≥ 125 BPM, ≥ 16 beats, < 30 seconds) and high degree AV block (2nd or 3rd degree, ≥ 8 beats) were chosen because they are significant prognostic indicators of depressed left ventricular ejection fraction and cardiac death [1]. The combined number of arrhythmic events in each group will be calculated along with the arrhythmia incidence rate defined as the percentage of patients in each group experiencing at least one of the defined arrhythmias of interest.

An exploratory sub-analysis will be conducted to determine the number and incidence rate of each separate arrhythmia type per dose group.

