4.2 Secondary Outcomes

Infarct size parameters will be assessed by CMR at 72 +/- 24 hours and 3 months; the following will be compared between groups; infarct size as a proportion of ventricular volume (INF/VV), myocardial salvage index (MSI) and absolute MI size.

- The proportion of patients with ST-segment resolution at 4 hours post study drug
- Serum levels of troponin calculated as AUC 0-48 hours post-study drug
- Persistent arrhythmias at 30 days and 3 months
- Measures of cardiac function by CMR including end-diastolic volume (EDV), end-systolic volume (ESV), fractional shortening (FS) and ejection fraction (EF).
- Serum biomarkers of cardiac injury, inflammation and remodeling
- Cardiac-related adverse events including the development of heart failure out to 3 months of follow up
- Incidence of all cause and cardiac mortality out to 6 months of follow up-to be assessed by phone call to patient or if

patient is unavailable, by medical records of physician/investigator.

Safety and Tolerability:

Physical examination including vital signs, laboratory measures to include clinical chemistry, hematology and thyroid function tests will be performed. Adverse Events (AEs) and Serious Adverse Events (SAEs) will be recorded.

12 lead ECGs will be performed at intervals at and post baseline.

Pharmacokinetics:

Plasma iodide levels will be measured in each patient. The concentration-time profile of plasma iodide will be derived for each of the groups. The pharmacokinetics of iodide will be described as area under the concentration versus time curve (AUC), the maximal concentration (C_{max}) and the time (T_{max}) when the maximal concentration is achieved. The terminal half-life ($T_{1/2}$), the total body clearance (CL), and the volume of distribution (V) will also be derived.

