7 STUDY TREATMENTS

7.1 Description of Study Drug

FDY-5301 is sodium iodide (chemical formula NaI) administered as an isotonic solution for intravenous injection with a concentration of 7.2 mg/mL. The dosage form of FDY-5301 is a small volume parenteral solution. The solution has a pH between 7.0 and 9.5. Normal saline will be used as placebo.

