12 ASSESSMENT OF PHARMACOKINETICS, TROPONIN AND LABORATORY SAFETY MEASURES

12.1 Pharmacokinetics: Blood Iodide Levels

12.1.1 Pharmacokinetic Evaluation

The concentrations of FDY-5301 will be measured in plasma. 6 mL of blood should be collected in a lithium heparin tube. Every effort should be made to collect the PK samples as close to the time points listed below.

- Pre-study drug
- 2 minutes, 1, 4, 24 and 48 hours post-study drug

The pharmacokinetic analysis will include calculations of concentration-time profiles in subjects following dosing with study drug. Mean, standard deviation (SD) and CV will be calculated at each time point. For each dose group, the pharmacokinetic behavior of blood iodide will be described as area under the concentration versus time curve (AUC, AUC_{inf}) the maximal concentration (C_{max}), the time (T_{max}) when the maximal concentration is achieved, the apparent terminal elimination rate (K_{el}) and terminal half-life (T_{1/2}) for each subject. From this information, the total body clearance (CL), and the volume of distribution (V) will be derived.

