11.6 Pharmacokinetic Assessment

11.6.1 Pharmacokinetic Analysis

The following PK parameters will be determined where possible from plasma iodide concentrations using non-compartmental methods performed using Phoenix WinNonlin (Version 6.4 or higher):

Parameter	Definition
AUC _{last}	area under the concentration-time curve from time 0 to the time of the last observed quantifiable concentration (T _{last}), calculated using the linear trapezoidal rule for increasing concentrations and the logarithmic rule for decreasing concentrations
AUC _{inf}	area under the concentration-time curve extrapolated to infinity calculated using the following equation: $AUC_{inf} = AUC_{last} + C_t/Kel$ where C _t is the last observed quantifiable concentration and Kel is the terminal elimination rate constant.
C _{max}	maximal observed plasma concentration
T _{max}	time when maximal concentration is achieved
T _{last}	time of last quantifiable concentration
Kel	apparent terminal elimination rate constant
T _{1/2}	apparent terminal elimination half-life, calculated as natural log (ln)(2)/Kel
CL	total body clearance
V _z	volume of distribution during the terminal elimination phase
V _{ss}	volume of distribution at steady-state

Additional PK parameters may be determined where appropriate. If the IV bolus model is used (refer to last bullet point in Section 11.6.4), then C₀ (back-extrapolated concentration at time zero) may be calculated by excluding the observed predose concentration value and then using a log-linear regression of the first 2 postdose data points to back-extrapolate to the concentration at time 0.

Pharmacokinetic analysis will, where possible, be carried out using actual postdose times recorded in the raw data. If actual times are missing, nominal times may be used with sponsor approval.

Concentrations will be used as supplied by the analytical laboratory for PK analysis. The units of concentration and resulting PK parameters, with amount or concentration in the unit, will be presented as they are received from the analytical laboratory.

The dose level of FDY-5301 (sodium iodide) will be converted to its free base equivalent for PK analysis if the analytical laboratory reports the free base concentration.

C_{max}, T_{max}, and T_{last} will be obtained directly from the plasma concentration-time profiles.

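### SAP 11.6.1 ties its only dose conversion to a 'free base' result, which sodium iodide cannot have. Depending on laboratory reporting and how the rule is read, CL, Vz and Vss are either right or about 18% too high.

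*SAP*

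**What the plan says.** **Dose.** Protocol 7.1 states "FDY-5301 is sodium iodide (chemical formula NaI) administered as an isotonic solution for intravenous injection with a concentration of 7.2 mg/mL". The Synopsis gives the dose levels on that basis: "FDY-5301 0.5 mg/kg, 1.0 mg/kg, 2.0 mg/kg or placebo will be administered intravenously (IV) by bolus injection".

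**Analyte.** SAP 11.6.1 says that the "PK parameters will be determined where possible from plasma iodide concentrations using non-compartmental methods". Protocol 4.2 agrees: "Plasma iodide levels will be measured in each patient". Protocol 12.1.1 words it differently, "The concentrations of FDY-5301 will be measured in plasma", and then refers to blood iodide later in the same section.

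**Matching dose to concentration.** On the concentration side nothing is rescaled: "Concentrations will be used as supplied by the analytical laboratory for PK analysis". On the dose side, SAP 11.6.1 has one rule. The FDY-5301 dose level, which the sentence itself identifies as sodium iodide, "will be converted to its free base equivalent for PK analysis if the analytical laboratory reports the free base concentration". No factor is stated, and there is no separate instruction for results reported as iodide. SAP section 13, on changes from the protocol analyses, does not mention the matter.

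**Parameters that use the dose.** SAP 11.6.1 lists CL, Vz and Vss. Protocol 4.2, 12.1.1 and 14.1.7 list CL and V.

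**The concern.** CL, Vz and Vss are each a dose divided by a measure of exposure. They are correct only if the dose and the concentrations refer to the same mass of the same species. Here the dose is a mass of NaI, the named analyte is iodide, and the concentrations are taken as supplied, so any matching has to be done on the dose.

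The one sentence that provides for this uses a term that does not fit the compound. 'Free base' belongs to salts of organic bases. NaI has none, and a laboratory that measures iodide has no reason to use the term. An analyst who follows the words finds the condition unmet and leaves the dose as NaI. An analyst who follows the apparent purpose converts it. Both could say that they had followed the SAP, and their clearances would differ by a constant factor. Because that factor is the same at every dose, comparing the dose groups would not reveal it.

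PK is one of the three stated purposes of the trial, and its reporting is descriptive (SAP 11.6.7), so the parameter values are themselves the result.

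**Working it through.** The documents give no molar mass, conversion factor or value of CL or V, so there is no planned figure to reproduce. The check is of the size of the mismatch.

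**Inputs**
- Chemical form NaI: Protocol 7.1.
- Doses 0.5, 1.0 and 2.0 mg/kg of FDY-5301: Protocol Synopsis.
- Sampling at 2 minutes and 1, 4, 24 and 48 hours: Protocol 12.1.1.
- Assumption, not in the documents: standard atomic masses Na 22.99 and I 126.90, anhydrous salt, so NaI = 22.99 + 126.90 = 149.89.

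**Step 1: which parameters depend on dose**
- CL = Dose / AUCinf
- Vz = Dose / (AUCinf × Kel)
- Vss = CL × MRT

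All three are proportional to dose. AUC, Cmax, Tmax, Kel, half-life and the back-extrapolated C0 come from the concentrations alone.

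**Step 2: the factor**
- Iodide fraction of NaI by mass: 126.90 / 149.89 = 0.847
- An NaI dose paired with iodide mass concentrations: 149.89 / 126.90 = 1.181, or +18.1%
- Doses as iodide: 0.5 × 0.847 = 0.423, 1.0 × 0.847 = 0.847 and 2.0 × 0.847 = 1.693 mg/kg (from the unrounded factor 0.8466)

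**Step 3: numerical confirmation**

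This used illustrative values chosen only for the check: CL 2 L/h, V 30 L, 80 mg NaI as a bolus, mono-exponential decline, at the protocol sampling times.
- Iodide dose: 80 × 0.8466 = 67.73 mg
- AUCinf of iodide: 67.73 / 2 = 33.87 mg·h/L
- Kel: 2 / 30 = 0.0667 per hour

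| Dose used | CL (L/h) | Vz and Vss (L) | Half-life (h) |
|---|---|---|---|
| Iodide, 67.73 mg | 67.73 / 33.87 = 2.00 | 30.0 | 10.4 |
| NaI, 80 mg | 80 / 33.87 = 2.36 | 35.4 | 10.4 |

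The ratio is 1.181 for CL, Vz and Vss. Half-life does not move.

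**Step 4: the outcome under each reading**

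| Laboratory reports | How the SAP rule is applied | Error in CL, Vz, Vss |
|---|---|---|
| Iodide by mass | Literally: no free base, dose left as NaI | +18.1% |
| Iodide by mass | 'Free base' read as iodide, dose converted | 0% |
| NaI (FDY-5301) equivalents | No conversion triggered | 0% |

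The factor is the same at all three dose levels, so ratios between dose groups are unchanged.

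**The case against.** The best answer is that the safeguard is already there. The sentence names this compound, and its evident purpose is to put the dose on the basis of the reported concentration. A competent pharmacokineticist would take 'free base' to mean the measured moiety and convert, leaving no error. The bioanalytical method is not among the documents, and Protocol 12.1.1 leaves open that results are reported as FDY-5301, in which case no conversion is needed. The consequences are also narrow. The Synopsis PK parameters (Cmax, AUC, Tmax and half-life) do not use the dose, no inferential PK analysis is planned (SAP 11.6.7), and a known constant can be corrected later by one multiplication.

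Most of this stands. A reader might infer that clearance and volumes will certainly be 18% too high, and the documents do not support that: it needs both iodide-mass reporting and a literal reading. A reader might also infer that the error would pass into later exposure modelling. The documents plan none. The only exposure analysis is a scatterplot of iodide AUCinf against INF/VV at 3 months (SAP 11.6.8), and it does not use the dose.

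What does not stand is that the intent makes the wording harmless. The SAP states that it supersedes the protocol's statistical considerations (SAP section 4), so its wording is what an analyst will follow. As written, that wording gives no usable trigger and no factor for the analyte that the plan names.

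**Conclusion.** The point holds as a minor correction. The dose-conversion rule in SAP 11.6.1 uses a term that does not apply to sodium iodide and does not say what to do when plasma iodide is reported as iodide. The error in CL, Vz and Vss is about 18% upward in every dose group if the laboratory reports iodide by mass and the rule is taken literally, and 0% otherwise. The 18% rests on standard atomic masses and anhydrous NaI; which case applies rests on the laboratory's reporting basis, which the documents do not settle. No primary, efficacy or safety conclusion depends on it.

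**What to change.** Replace the conversion sentence in SAP 11.6.1 with: 'If plasma concentrations are reported as iodide mass, the administered dose will be expressed as iodide (mg NaI × 0.847) for CL, Vz and Vss; if reported as NaI equivalents, no conversion is made.' State the reporting basis in the PK tables.

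Both branches are needed. Converting the dose when results are already NaI equivalents would understate the same parameters by 1 − 126.90/149.89 = 15.3%.

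The cost is one sentence and a table note, with no new data or samples. It should be done before database lock, by which time SAP section 4 requires the plan to be final.

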11.6.3 Criteria for the Calculation of an Apparent Terminal Elimination Half-Life

11.6.3.1 Number of Data Points

- At least three data points will be included in the regression analysis and preferably should not include C_{max} .

11.6.3.2 Goodness of Fit

- When assessing terminal elimination phases, the adjusted coefficient for the determination of exponential fit (R^2 adjusted) will be used as a measure of the goodness of fit of the data points to the determined line.
- Kel and Kel -based parameters will only be calculated if the R^2 adjusted value of the regression line is greater than or equal to 0.7.

11.6.3.3 Period of Estimation

- Apparent terminal elimination half-life will be estimated over a time period of at least two half-lives, where possible.
- Where $T_{1/2}$ is estimated over a time period of less than two half-lives, it will be flagged in the data listings at the discretion of the Pharmacokineticist, and the robustness of the value should be discussed in the study report.

11.6.4 Calculation of AUC

- The minimum requirement for the calculation of AUC will be the inclusion of at least 3 consecutive plasma concentrations above the lower limit of quantification (LLOQ), with at least 1 of these concentrations following C_{\max} .
- For any partial AUC determination, nominal time will generally be used for the end of the interval. Actual times for partial AUC intervals may be used at the discretion of the Pharmacokineticist.
- AUC_{inf} values where the percentage extrapolation is less than 20% will be reported. AUC_{inf} values where the percentage extrapolation is between 20 to 30% will be reported, flagged, and included in the descriptive statistics, while AUC_{inf} values where the percentage extrapolation is greater than 30% will be reported and flagged, but excluded from descriptive statistics.
- If an IV bolus model is used, and if the combined area of back-extrapolated and infinity-extrapolated is $>30\%$, AUC_{inf} may not be reported or a different model may be used (such as the infusion model), at the discretion of the Pharmacokineticist.

11.6.5 Anomalous Values

- If a value is considered to be anomalous due to being inconsistent with the expected PK profile, it may be appropriate to exclude this point from the PK analysis. However, the exclusion of data must have strong justification and will be documented in the raw data and study report.
- Embedded BLQ values may be considered anomalous depending on the route of administration and the characteristics of the drug.

11.6.6 Presentation of Pharmacokinetic Data

11.6.6.1 Presentation of Pharmacokinetic Plasma Drug Concentration Data

- The following rules will be applied if there are values that BLQ or if there are missing values (e.g., no result [NR]) in a plasma concentration data series to be summarized.
 - For the calculation of summary statistics, BLQ values will be set to zero.
 - If an embedded BLQ value is considered anomalous within the concentration-time profile, this value will be excluded from the summary statistics.
 - Where there is NR, these will be set to missing.
 - If there are less than 3 values in the data series, only the min, max and N will be presented. The other summary statistics will be denoted as not calculated (NC). BLQ is considered a value.

- If all the values are BLQ, then the arithmetic mean, arithmetic SD, median, min and max will be presented as zero, and the geometric mean and geometric CV% will be denoted as NC.
- If the value of the arithmetic mean or median is BLQ, it will be presented as zero, and the geometric mean and geometric CV% will be denoted as NC.

11.6.6.2 Presentation of Pharmacokinetic Parameters

- For the calculation of summary statistics of PK parameters, all NR and NC values in a data series will be set to missing.
- The AUC values will be set to NC if they have been calculated using fewer than 3 concentrations, and/or 3 concentrations if the last is C_{max} .

11.6.7 Pharmacokinetic Statistical Methodology

All PK analyses will be performed with the PK population.

All reportable plasma iodide concentration data and derived PK parameters will be summarized by treatment and listed.

Plasma concentrations and derived PK parameters will be summarized in terms of N, arithmetic mean, SD, median, minimum, maximum, geometric mean and geometric CV%. For the PK parameter T_{max} and T_{last} , the descriptive statistics will not include geometric mean, and geometric CV%. Individual figures will also be presented using actual sampling times.

There are no formal inferential statistical analyses planned.

11.6.8 Pharmacokinetic/Efficacy Analysis

A scatterplot will be produced to evaluate potential correlations between the Iodide plasma AUC_{inf} and INF/VV at 3 months post-study drug.

12 INTERIM ANALYSES

After the 14 day follow-up visit to the clinic, all patients' data will be collected and analyzed for:

- Safety (14-day arrhythmias)

After the 3 month follow up visit, analysis of the following will occur:

- Early efficacy outcomes including MSI, INF/VV, INF
- Serum troponin AUC_{0-48} hours post-study drug
- ST-segment resolution by 4 hours post-study drug

- Cardiac function including EDV, ESV, FS and EF

All remaining assessments will be analyzed at the conclusion of the study.

13 CHANGES FROM THE PROTOCOL SPECIFIED STATISTICAL ANALYSES

For the analysis of arrhythmias of interest, a person-time adjustment will be applied to account for potential missing data during the 14-day monitoring period, due to possible unforeseen reasons such as patient withdrawal, device failure or death. The incidence rate for each treatment group (and overall FDY-5301) will be calculated as the number of events divided by the total person-time of monitoring within each treatment group. The incidence rate ratios of each treatment group (and overall FDY-5301) versus the placebo will be derived.

Scope of the interim analyses has been updated.

Overall summary for primary and exploratory safety and efficacy endpoints will be summarized by stratification of TIMI flow grade and infarct location

14 DATA PRESENTATION

14.1 Insufficient Data for Presentation

Some of the TFLs may not have sufficient numbers of patients or data for presentation. If this occurs, the blank TFL shell will be presented with a message printed in the center of the table, such as, “No serious adverse events occurred for this study.”

[figure not shown]
